5.4. Subgroups

Subgroup analyses of safety will be performed for the following patient demographics and other factors.

- Hepatic impairment
- Renal impairment
- Children (<15 years), adults (≥15 to <65 years), elderly (≥65 years)
- Age [<65 years, ≥65 to <70 years, ≥70 to <75 years, ≥75 to <80 years, ≥80 to <85 years, ≥85 years]
- Sex [male, female]
- Inpatient/outpatient status at the initial prescription [inpatient, outpatient]
- Body weight at the start of treatment (by sex) [<40 kg, ≥40 to <50 kg, ≥50 to <60 kg, ≥60 kg]
- Name of target disease (i.e., diagnosis of neuropathic pain) [by disease name]
- Hemodialysis [no, yes]
- Creatinine clearance [<15 mL/min, ≥15 to <30 mL/min, ≥30 to <60 mL/min, ≥60 mL/min]
- Past medical history [no, yes]
- Complications [no, yes]
- Prior medications [no, yes]
- Concomitant medications [no, yes]
- Non-medication therapies [no, yes]
- Timing of drug administration (at the start of treatment) [before meal, after meal, other]
- Daily dose (at the start of treatment) [≤25 mg, >25 to ≤75 mg, >75 to ≤150 mg, >150 to ≤300 mg, >300 to ≤600 mg, >600 mg]

- Daily dose (maximum) [≤ 25 mg, >25 to ≤ 75 mg, >75 to ≤ 150 mg, >150 to ≤ 300 mg, >300 to ≤ 600 mg, >600 mg]
- Pregnant and parturient women (pregnant)

Subgroup analyses of efficacy will be performed for the following patient demographics and other factors.

- Hepatic impairment
- Renal impairment
- Children (<15 years), adults (≥ 15 to <65 years), elderly (≥ 65 years)
- Age [<65 years, ≥ 65 to <70 years, ≥ 70 to <75 years, ≥ 75 to <80 years, ≥ 80 to <85 years, ≥ 85 years]
- Sex [male, female]
- Inpatient/outpatient status at the initial prescription [inpatient, outpatient]
- Body weight at the start of treatment (by sex) [<40 kg, ≥ 40 to <50 kg, ≥ 50 to <60 kg, ≥ 60 kg]
- Name of target disease (i.e., diagnosis of neuropathic pain) [by disease name]
- Hemodialysis [no, yes]
- Creatinine clearance [<15 mL/min, ≥ 15 to <30 mL/min, ≥ 30 to <60 mL/min, ≥ 60 mL/min]
- Past medical history [no, yes]
- Complications [no, yes]
- Prior medications [no, yes]
- Concomitant medications [no, yes]
- Timing of drug administration (at the start of treatment) [before meal, after meal, other]
- Daily dose (at the start of treatment) [≤ 25 mg, >25 to ≤ 75 mg, >75 to ≤ 150 mg, >150 to ≤ 300 mg, >300 to ≤ 600 mg, >600 mg]
- Daily dose (maximum) [≤ 25 mg, >25 to ≤ 75 mg, >75 to ≤ 150 mg, >150 to ≤ 300 mg, >300 to ≤ 600 mg, >600 mg]

6. Endpoints and covariates

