8.1.3. Analysis of binary data

Frequency and its proportion will be calculated. If the confidence interval of proportion is calculated, a 2-sided 95% confidence interval (exact method) will be calculated.

If the proportion is compared between subgroups, Fisher’s exact test and Cochran-Armitage test (exact method) will be performed for the relationships with nominal scale data and

ordinal scale data, respectively, and the risk ratio and risk difference with their 95% confidence intervals will be calculated.

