8.2.2. Patient demographics and treatment history

- **Patient demographics**

The following patient demographics will be tabulated in the safety analysis set and efficacy analysis set in accordance with Section 8.1.

- Sex [male, female]
- Age at the start of treatment (continuous data)
- Age category at the start of treatment [<15 years, ≥15 to <65 years, ≥65 years]
- Age category at the start of treatment [<65 years, ≥65 to <70 years, ≥70 to <75 years, ≥75 to <80 years, ≥80 to <85 years, ≥85 years]
- Inpatient/outpatient status at the initial prescription [inpatient, outpatient]
- Height at the start of treatment (by sex) (continuous data)
- Body weight at the start of treatment (by sex) (continuous data)
- Body weight category at the start of treatment (by sex) [<40 kg, ≥40 to <50 kg, ≥50 to <60 kg, ≥60 kg]
- Name of target disease (i.e., diagnosis of neuropathic pain) [by disease name]
- Duration of target disease (i.e., diagnosis of neuropathic pain) (continuous data)
- Severity of target disease (i.e., diagnosis of neuropathic pain) [mild, moderate, severe]
- Pain score (continuous data)
- Name of underlying disease (i.e., primary disease of nerve damage that cause neuropathic pain) [by disease name]
- Hepatic impairment [no, yes (mild, moderate, severe)]
- Renal impairment [no, yes (mild, moderate, severe)]
- Hemodialysis [no, yes]
- Creatinine clearance category [<15 mL/min, ≥15 to <30 mL/min, ≥30 to <60 mL/min, ≥60 mL/min]
- Hyperalgesia [no, yes]
- Past medical history [no, yes]
- Complications [no, yes]

The following number and proportion of patients will be tabulated by SOC and PT in the safety analysis set.

- Breakdown of underlying disease
- Breakdown of past medical history
- Breakdown of complications

The following number and proportion of patients will be tabulated in the safety analysis set and efficacy analysis set.

- Presence or absence and breakdown of concomitant medications
- Presence or absence and breakdown of concomitant non-medication therapies
- Presence or absence and breakdown of prior medications

- **Information on administration of Lyrica**

The following information on administration of Lyrica will be tabulated in the safety analysis set.

- Duration of administration [≤ 4 weeks, >4 to ≤ 13 weeks, >13 to ≤ 26 weeks, >26 to ≤ 52 weeks, >52 to ≤ 78 weeks, >78 to ≤ 104 weeks, >104 weeks]
- Timing of administration (at the start of treatment) [morning, noon, evening, bedtime, other]

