For “peripheral edema and edema-related events”, number and proportion of patients with events will be tabulated by presence or absence of weight increase. Two types of definitions of patients with weight increase are used: 1) those with “weight increased (MedDRA PT)” reported as an adverse reaction; 2) those with body weight increased by 7% or more from baseline at least once. Number and proportion of patients with adverse reactions will be tabulated for each SOC and PT by presence or absence of peripheral edema. In addition, number and proportion of patients with the following adverse reactions will be tabulated by presence or absence of peripheral edema to evaluate the relationship between peripheral edema and cardiovascular and respiratory events.

^a: Occurrence of cardiovascular and respiratory events will be examined in patients with peripheral edema and edema-related events.

- Events coded to the MedDRA PT “arrhythmia”, “atrial fibrillation”, “cardiovascular disorder”, “cardiac failure congestive”, “hypertension”, “hypotension”, “palpitations”, “tachycardia”, or “dyspnoea”
 - Events coded to the MedDRA SOC “Cardiac disorders”, “Vascular disorders”, or “Respiratory, thoracic and mediastinal disorders”
- **Pancreas-related events, thyroidal function-related events, change in appetite and activity-related events, suicide-related events, withdrawal symptom and rebound phenomenon-related events, and skin disorder-related events**

Number and proportion of patients will be calculated for each event.

- **Patients with special background**

Number and proportion of patients with adverse reactions and serious adverse reactions will be calculated by SOC and PT in the following subgroups and other patients.

- Elderly patients
- Pediatric patients
- Patients with renal impairment
- Patients with hepatic impairment

Patients with renal impairment are defined as those with “Renal impairment: yes” or creatinine clearance of less than 60 mL/min.

- **Relationship between dosage and administration and development of adverse reactions**

In order to evaluate the relationship between dosage and administration and development of adverse reactions, number and proportion of patients with adverse reactions will be tabulated by SOC and PT for patients whose creatinine clearance and the initial daily dosage are ≥ 60 mL/min and 150 mg, respectively, and patients whose creatinine clearance and the initial daily dosage are ≥ 30 to < 60 mL/min and 75 mg, respectively.

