- **Relationship between prior and concomitant medications and development of adverse reactions**

In order to evaluate the relationship between the drug class of prior or concomitant medications and adverse reactions, number of patients with adverse reactions will be tabulated for each PT by target disease (i.e., diagnosis of neuropathic pain) and drug class of prior or concomitant medications. However, concomitant medications used after the initial onset of the event will be excluded from tabulation. For target disease, diseases with number of patients analyzed of approx. 100 or more will be examined.

- **Occurrence of adverse reactions by inclusion in/exclusion from the safety analysis set**

A listing of adverse reactions in patients excluded from the safety analysis set will be prepared. Moreover, number of patients with adverse reactions will be tabulated by SOC and PT.

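### The drug-class table in SAP 8.2.3.1 counts patients with reactions but gives no users, non-users or proportions, so it cannot evaluate the relationship it names

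*SAP*

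**What the plan says.** In SAP 8.2.3.1, the item on prior and concomitant medications opens with its purpose: "In order to evaluate the relationship between the drug class of prior or concomitant medications and adverse reactions". For this it plans that the "number of patients with adverse reactions will be tabulated for each PT by target disease" and drug class. Two restrictions follow:

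- On exposure: "concomitant medications used after the initial onset of the event will be excluded from tabulation".
- On strata: "diseases with number of patients analyzed of approx. 100 or more will be examined".

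The item just before it in the same section, on dosage, is also described as evaluating a relationship. There the plan is that the "number and proportion of patients with adverse reactions will be tabulated by SOC and PT for patients whose creatinine clearance" and starting dose fall in given groups.

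**The concern.** A relationship between a drug class and a reaction is a comparison of risk in users with risk in non-users. The planned table holds only the cases. Its counts rise with the risk in users and also with how often the class is prescribed, and nothing in the table separates the two.

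The exposure rule adds a second difficulty for anyone who supplies the missing denominators afterwards. A patient with the event loses concomitant drugs used after onset. A patient without the event has no onset date, and the SAP sets no matching date for such patients. Whole-period user numbers would therefore measure exposure over a longer stretch in event-free patients than in cases.

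At stake is the reading of possible drug combinations in a survey whose objective is long-term safety and whose final analysis supports the reexamination application. A common class could draw attention it does not deserve, and a rarer class with a higher risk could be passed over.

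**Working it through.** **Figures in the plan.** The SAP attaches no figure to this table. Its one sample-size statement (310 patients, incidence 0.97%, at least 95% probability of one case) reproduces: 1 − (1 − 0.0097)^310 = 0.951. It has no bearing on the point.

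**Step 1: does another section supply the comparison?**

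| SAP section | What it gives | What is still missing |
|---|---|---|
| 8.1.3 | General rule for binary data: "Frequency and its proportion will be calculated" | Which denominator: users of the class, all patients with the disease, or cases |
| 8.2.2 | "Presence or absence and breakdown of concomitant medications", and the same for prior medications, in the analysis sets | Not stated by target disease; no onset cut-off |
| 5.4 and 8.2.3.4 | Any prior or any concomitant medication, yes or no, with tests, risk ratios and risk differences | Not by drug class |
| 8.2.3.1, stratum rule | About 100 or more patients per disease | A disease total, not the users of a class |

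None gives users and non-users by class and disease alongside the reactions.

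**Step 2: counts alone.** Take 12 cases in each of two classes (hypothetical). With 40 users, 12/40 = 30%. With 120 users, 12/120 = 10%. The planned table shows the same entry for a threefold difference in risk.

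**Step 3: one-sided cut-off, worked by hand.** Suppose the class has no effect (true risk ratio 1). Let b be the share using it at the start, s the share starting it on treatment, p the reaction risk, and q the probability that a starter has begun before onset. All values are assumptions; the SAP gives none.

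- Inputs: b = 0.20, s = 0.20, p = 0.20, starts uniform over 104 weeks, everyone followed to Week 104. Half of onsets fall uniformly in Weeks 0–13 (mean 6.5) and half in Weeks 13–104 (mean 58.5).
- q = 0.5 × 6.5/104 + 0.5 × 58.5/104 = 0.3125
- Cases still counted as exposed: p(b + sq) = 0.20 × (0.20 + 0.0625) = 0.0525
- Cases that lose their exposure: ps(1 − q) = 0.20 × 0.20 × 0.6875 = 0.0275

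The apparent risk ratio depends on where those lost cases go:

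- Whole-period users and non-users as denominators, lost cases counted among non-users: (0.0525/0.40) ÷ (0.1475/0.60) = 0.131/0.246 = 0.53
- Lost cases moved to the non-users in numerator and denominator: (0.0525/0.3725) ÷ (0.1475/0.6275) = 0.141/0.235 = 0.60
- Lost cases left out of both numerators: 0.131/0.20 = 0.66

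With s = 0 the exposed risk is pb/b = p and the ratio is 1.00. Drugs in use at the start are therefore not biased. Prior drugs are outside the cut-off altogether.

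**Step 4: with patients stopping treatment.** A simulation of 3,000,000 patients with no association used constant rates: reaction risk 20% over 104 weeks of treatment, stopping after Week 13 with 40% still treated at Week 104. Cases were classified at onset and event-free patients by their whole observed period, as in the second variant of Step 3.

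| In use at start | Start over 104 weeks | Apparent risk ratio |
|---|---|---|
| 10% | 20% | 0.77 |
| 10% | 30% | 0.72 |
| 20% | 20% | 0.84 |
| 20% | 30% | 0.78 |
| 30% | 20% | 0.87 |
| 30% | 30% | 0.82 |

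Classifying every patient by use at the start returns 1.00 in each setting.

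**Step 5: would deleting the cut-off help?** No. Keep the Step 3 inputs, drop the cut-off, and let 20% of reactions be treated with a drug of the class. A class with no effect then shows a risk ratio of about 1.47.

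**The case against.** The strongest reply is that this is one descriptive table. SAP 4.1 calls all testing exploratory, 4.2 sets no decision rule, and 8.2.3.5 allows further safety analyses. The formal medication comparison is the yes/no subgroup analysis, and 8.2.2 gives some medication user numbers. If target disease shows a significant difference, 8.2.3.4 appears to add a medication breakdown by disease as well. This limits the consequence. It does not repair the table: the yes/no comparison is not by class, and the breakdowns carry no matching exposure rule.

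A reader might infer that the table leans towards a protective effect, or that any ratio formed from it is biased. The SAP does not support either reading. A table of counts contains no ratio that could lean. The bias appears only when someone adds user numbers that were not cut off in the same way, and then only for concomitant drugs started during treatment.

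A reader might also take the cut-off itself as the error. It has a sound purpose, and Step 5 shows what happens without it. The weakness is that it has no counterpart for event-free patients.

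Finally, every rate in Steps 3 and 4 is assumed. That objection stands in full as regards the size of the bias.

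**Conclusion.** The point holds on the missing denominators, and this part needs no assumption. Followed as written, the table cannot separate risk from frequency of prescribing and so cannot do what its opening sentence promises.

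The exposure rule is a conditional problem. If the counts are compared with whole-period user numbers, a class with no effect shows a risk ratio below 1 to the extent that its use begins on treatment. The direction is firm; the size is not. It is about 0.72 to 0.87 under the Step 4 assumptions. With the Step 3 model it falls to 0.29 if 10% use the class at the start, 30% start later and 70% of onsets come by Week 13, and it is 1.00 if no use begins on treatment.

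The consequence is limited by the descriptive, exploratory status of the analysis. The correction is still worth making because it is cheap.

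**What to change.** Revise this item of SAP 8.2.3.1 as follows.

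1. For each target disease and drug class, give the number of patients exposed, the number with the reaction (by PT) and the proportion, beside the same three figures for patients not exposed.
2. Define exposure identically for patients with and without the event: prior drugs, and drugs in use at the start of Lyrica.
3. Keep drugs started later as a separate descriptive count with the existing onset cut-off, labelled as not for comparison. Optionally, analyse them as reactions per patient-year on and off the class.
4. State whether the cut-off removes only drugs first taken after onset, or also drugs begun before onset and continued. The present wording can be read either way, and the second reading would remove more exposed cases.

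The cost is a change of wording and extra table columns. The existing cut-off already requires drug and onset timing, so no new data should be needed for the comparison at the start of treatment. The downside is that drugs started later leave the main comparison unless the person-time analysis is done.

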8.2.3.2. Adverse events

- **All adverse events**

Number and proportion of patients with adverse events will be tabulated by SOC and PT.

- **Adverse events by serious/non-serious**

Number and proportion of patients with serious adverse events will be tabulated by SOC and PT. Non-serious adverse events will be tabulated in the same manner.

8.2.3.3. Other endpoints

- **Body weight**

Summary statistics specified in Section 8.1.1 will be calculated by time point as defined in Appendix 1 for measurements and their changes from baseline.

Number and proportion of patients with the following adverse reactions will be tabulated for patients whose body weight increased by 7% or more from baseline at least once and other patients.

- Abnormal glucose tolerance-related events: Events coded to the MedDRA HLGT “glucose metabolism disorders (incl diabetes mellitus)” or the MedDRA HLT “carbohydrate tolerance analyses (incl diabetes)”
- Dyslipidemia-related events: Events coded to the MedDRA HLGT “lipid metabolism disorders” or “lipid analyses”
- Events coded to the MedDRA PT “arrhythmia”, “atrial fibrillation”, “cardiovascular disorder”, “cardiac failure congestive”, “hypertension”, “hypotension”, “palpitations”, “tachycardia”, or “dyspnoea”
- Events coded to the MedDRA SOC “Cardiac disorders”, “Vascular disorders”, or “Respiratory, thoracic and mediastinal disorders”

- **Laboratory parameters**

Summary statistics specified in Section 8.1.1 will be calculated by time point as defined in Appendix 1 for laboratory parameters and their changes from baseline.

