5.1. Safety analysis set

The safety analysis set is the full analysis set that is as close to all patients treated with Lyrica as possible. More specifically, the safety analysis set is defined as the population of registered or reported patients, excluding those who meet any of the following conditions.

- a. The survey form could not be collected at all (description in the report: “survey form not collected”).
- b. There was a contract violation or deficiency (description in the report: “contract violation/deficiency”).
- c. There was a registration violation (description in the report: “registration violation”).
- d. Administration of Lyrica under survey has not been reported at all (description in the report: “no administration information”).
- e. Information on adverse events has not been reported at all - no visits after the day of initial prescription (description in the report: “no adverse event information - no revisit”).
- f. Information on adverse events has not been reported at all - adverse events not described (description in the report: “no adverse event information - not described”).

Detailed handling of patient inclusion in/exclusion from the analysis set should be in accordance with patient inclusion/exclusion criteria separately specified.

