6.4. Covariates

For safety and efficacy of Lyrica, no covariates or potential covariates are identified from clinical study data, etc. obtained to date.

7. Handling of missing data

If the seriousness/outcome of adverse events and action taken with Lyrica for the adverse events are missing, they will be handled as “unknown” at tabulation.

If body weight is not measured within the acceptable range at each time point (Appendix 1), it will be handled as missing and will not be imputed.

If data on efficacy evaluation (clinical efficacy) at Week 104 (or at discontinuation/completion of treatment) are missing, the data will be handled as missing even when the results of evaluation at Week 26, 52, or 78 are available. The missing data will not be imputed.

8. Statistical methods and statistical analyses

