10.1. Appendix 1: Details of data extraction

A1.1 Data to be used for tabulation and analysis

Data collected after the safety evaluation date will not be used in tabulation and analysis specified in this plan. Data on efficacy endpoints (Section 6.2) will be used even if they are collected after the safety evaluation date.

A1.2 Definition of visit schedule

Visit schedule	Endpoint	Definition [acceptable window]
Start of treatment	Laboratory tests and body weight	From 30 days before the first dose (date of start of treatment) in the survey to the date of start of treatment (Day 1)
After 4 weeks	Laboratory tests and body weight	Day 29 [Day 2 to Day 60]
After 13 weeks	Laboratory tests and body weight	Day 92 [Day 61 to Day 137]
After 26 weeks	Laboratory tests and body weight	Day 183 [Day 138 to Day 273]
After 52 weeks	Laboratory tests and body weight	Day 365 [Day 274 to Day 455]
After 78 weeks	Laboratory tests and body weight	Day 547 [Day 456 to Day 637]
After 104 weeks	Laboratory tests and body weight	Day 729 [Day 638 to Day 819]

If multiple data are collected within the acceptable window, the data whose date of evaluation is closer to the definition will be used for tabulation and analysis. If the difference from the definition is the same, the newer data will be used.

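### Patients with no usable weight change are counted with those who did not gain 7%, so the comparison group mixes measured non-gainers with never-assessed patients

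*SAP*

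**What the plan says.** Section 8.2.3.3 plans counts of glucose, lipid, cardiovascular and respiratory reactions in two groups. They "will be tabulated for patients whose body weight increased by 7% or more from baseline at least once and other patients".

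For edema, section 8.2.3.1 states that "number and proportion of patients with events will be tabulated by presence or absence of weight increase". The second of its two definitions of weight increase is "those with body weight increased by 7% or more from baseline at least once". There is no third level in either place.

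Three other parts of the SAP bear on who enters the split:

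- Section 5.1: "the safety analysis set is defined as the population of registered or reported patients, excluding those who meet any of the following conditions". None of conditions a to f concerns body weight, and section 5.3 defines no further analysis set.
- Section 7: "If body weight is not measured within the acceptable range at each time point (Appendix 1), it will be handled as missing", with no imputation. The rule applies to a value at a time point.
- Appendix 1, A1.2: the start-of-treatment weight must be dated "From 30 days before the first dose (date of start of treatment) in the survey" up to Day 1. The later windows run without a gap from Day 2 to Day 819.

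**The concern.** A gain of 7% can be shown or ruled out only in a patient with a baseline weight and at least one later weight. The SAP's second group is simply everyone not in the first. It therefore combines patients who were weighed and did not gain 7% with patients for whom the question cannot be answered. For example, if baseline is the Appendix 1 start-of-treatment value, a patient first weighed on Day 2 has no baseline and is counted as a non-gainer, whatever happens to the weight afterwards.

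These tables are meant to show whether weight gain goes together with metabolic and cardiorespiratory reactions and with edema, which is a major investigation item. If unweighed patients have a different recorded reaction risk, the contrast moves for reasons unrelated to weight. If they have the same risks and include some true gainers, the contrast is diluted.

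**Working it through.** **Reading the rules together.** The split in 8.2.3.3 is a criterion and its complement. A patient without a calculable change does not meet the criterion and so belongs to the complement. Section 5.1 does not remove that patient. Section 7 makes the weight missing at each time point but sets no denominator for an at-least-once classification. The same section gives missing seriousness, outcome and action taken an unknown category, but does nothing similar here.

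**Inputs.** The SAP has no figure on this point to reproduce. Its target of 310 is used below only for sampling noise, and it agrees with its own rationale: 1 - (1 - 0.0097)^310 = 0.951. Everything else is assumed:

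- u, share without usable weights: 5%, 10%, 30% or 50%
- g, share gaining 7% or more: 10% to 20%
- reaction risks as stated in each case

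**Composition.** Share of the comparison group never assessed = u / [(1-u)(1-g) + u].

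**Case 1: no true link.** Risk is rw = 20% in patients with usable weights, gainers or not, and ru in those without.

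Comparison-group risk = [(1-u)(1-g)rw + u·ru] / [(1-u)(1-g) + u]; apparent ratio = rw / that risk.

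Example with u = 0.3, g = 0.2, ru = 0.10: (0.112 + 0.030) / 0.86 = 0.165, and 0.20 / 0.165 = 1.21.

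**Case 2: weights missing at random, true ratio 2.0** (risk 20% in gainers, 10% in non-gainers).

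Comparison-group risk = [(1-g)·0.10 + g·u·0.20] / [(1-g) + g·u]; apparent ratio = 0.20 / that risk.

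Example with u = 0.3, g = 0.2: (0.080 + 0.012) / 0.86 = 0.107, and 0.20 / 0.107 = 1.87.

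| u | Never assessed, share of comparison group | Case 1, ru = 10% (truth 1.00) | Case 1, ru = 30% (truth 1.00) | Case 2 (truth 2.0) |
|---|---|---|---|---|
| 5% | about 6% | 1.03 | 0.97 | 1.98-1.99 |
| 10% | 11-12% | 1.06 | 0.94-0.95 | 1.95-1.98 |
| 30% | 32-35% | 1.19-1.21 | 0.85-0.86 | 1.87-1.94 |
| 50% | 53-56% | 1.36-1.38 | 0.78-0.79 | 1.80-1.90 |

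Ranges run over g = 10% to 20%. In Case 1 with ru = 20% the ratio is 1.00 throughout.

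**Sampling noise.** With 310 patients, u = 30% and g = 15%, there are 310 × 0.7 × 0.15 = 32.6 gainers. A proportion of 20% then has a 95% half-width of 1.96 × √(0.2 × 0.8 / 32.6) = 0.137, about 14 points. In Case 1 with ru = 10% the comparison-group risk is 0.149 / 0.895 = 0.1665, a gap of about 3.4 points.

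**Limit of restricting to weighed patients.** Suppose no true link, a reaction risk of 20%, and weighing that depends on both outcomes: 95% / 80% of reactors with / without gain, and 70% / 50% of non-reactors. Risk in weighed gainers is 0.19 / 0.75 = 0.2533.

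- Planned split: 0.2533 / 0.1957 = 1.29 (g = 10%) or 0.2533 / 0.1906 = 1.33 (g = 20%).
- Restricted comparison: weighed non-gainers have 0.16 / 0.56 = 0.2857, so the ratio is 0.89.

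Restriction does not remove bias from selective weighing.

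**The case against.** The strongest reply is that much of this is visible or unlikely.

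- **Visibility.** Section 8.2.3.3 also plans summaries of weight change by time point, and section 8.1.1 includes the number of patients in such summaries. The safety-set total minus the largest of these counts is an upper bound on the number without a usable pair of weights. The baseline-weight tables (8.2.2, 8.2.3.4) give by subtraction the number without a baseline weight and their any-reaction proportion. This stands. It still does not give the exact number without any later weight, or the rates of the specific event groups in unassessed patients. Those would have to be rebuilt patient by patient from the section 9 listings.
- **Reading.** A programmer could take the no-imputation rule in section 7 as a reason to leave unweighed patients out, since counting them as non-gainers in effect imputes no gain. The tension is real, but the section 7 rule concerns single time points, while 8.2.3.3 states a two-way split with no exception. Section 5.1 refers to separately specified inclusion criteria, but those concern the analysis set.
- **Few patients exposed.** The windows are unbroken from Day 2 to Day 819, and the survey covers patients still on treatment after Week 13, so having no later weight at all means never being weighed over a long span. This narrows that route. A missing baseline weight remains.
- **Consequence.** The magnitudes rest on assumptions, noise can exceed the effect, no test is specified for these tables, and section 4.1 calls the survey's testing exploratory. All of this stands and sets the weight of the point.

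**Conclusion.** The concern holds on the SAP's wording. The comparison group in 8.2.3.3, and under the second definition in 8.2.3.1, includes patients whose weight change was never assessable, and no rule takes them out. The direction of the resulting bias is not fixed and its size cannot be known from the document. It is negligible if nearly all patients have usable weights and modest at 10% without them. At 30% or more it is large enough to mislead a reader, provided reaction risk differs clearly between weighed and unweighed patients. Because the tables are descriptive, the harm is to how they are read. The change is worth making because it is inexpensive.

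**What to change.** In section 8.2.3.3, and for the second definition of weight increase in section 8.2.3.1, add a sentence limiting the comparison of gains of at least 7% with smaller or no gains to patients who have a baseline weight and at least one post-baseline weight in the Appendix 1 windows. Show all other patients in a separate not-evaluable column with their event counts, and report the number of patients in each of the three columns.

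The cost is one sentence in each of two sections, one table column, and smaller denominators in the comparison. The change takes never-assessable patients out of the comparison group and shows how many there are. It does not correct for gains that occur between or after weighings, or for selective weighing.
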